- Number of health facilities: Khairahani health posts 3, private hospitals 5, government hospitals 1, urban health centre 9; Rapti – health post 5, community health unit 1, hospital 1, basic health service centres 7.

Design

The study design is a parallel two-arm pilot cluster-randomised controlled trial with schools as the unit of clustering. The rationale for using cluster randomisation rather than individual randomisation is that we seek to mitigate contamination resulting from intervention participants using their skills and sharing knowledge to improve their wider social environment. Moreover, cluster randomisation will mitigate potential conflict within schools

where participants and their families perceive individual allocation to the intervention or control condition to be inequitable.

Figure 3 is a flowchart of the trial. The trial will be conducted in eight schools (four intervention and four control). We will assess participants in intervention and control arms at baseline, after the second group session (Midline 1), after the sixth group session (Midline 2), at endline (within two weeks of the final group session) and at follow-up (12 weeks after the final group session). Figure 4 shows the timing of assessments. Midline surveys will enable us to explore how intermediate outcomes change in relation to the primary outcome. Through the follow-up we will assess if any change in symptoms is sustained beyond the intervention. The primary analysis in the phase III trial will be a cross-sectional comparison of mean depressive symptom scores at follow-up across trial arms, adjusted for baseline scores and potential confounders, and accounting for strata and clustering.

Inclusion/exclusion criteria

Eligible participants will be:

- adolescent boys and girls aged 13-19;
- attending a participating school;
- enrolled in class 8, 9 or 11;
- with depression (i.e. scoring 11 or more on the PHQ-A); and
- with functional impairment (i.e. scoring 4 or more on the functional impairment tool).

Adolescents will be excluded if they:

- are in class 10 or 12 because they are busy preparing for School Education and Plus 2 exams;
- are in class 7 and therefore may be too young to benefit from IPT;
- have suicidality (current plan or recent attempt in the past three months) because these adolescents require more acute, intensive treatment; or

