Randomisation will be at the school level and stratified according to whether recruitment at the school includes adolescents from class 11 or not. In total there will be three strata: Strata 1 will comprise two of the four schools from which we are recruiting adolescents in class 8, 9 and 11. Strata 2 will comprise the two remaining schools in class 8, 9 and 11. Strata 3 will comprise schools where we are recruiting in class 8 and 9 only. We will complete screening and the baseline survey in Strata 1 (which will take approximately two weeks) then randomise these schools with a 1:1 allocation ratio to the intervention and control arms. The intervention will then start in these schools. After Strata 1 schools have been allocated, screening and baseline will start in Strata 2 after which these schools will be randomly allocated to the intervention and control arms. The process will then be repeated in Strata 3. In Strata 1 and 2 there are two schools with four groups per school (eight adolescents per group): one male and one female group for Class 8 and 9 combined, one male and one female group for Class 11. In Strata 3 there are four schools with two groups per school: one male and one female for Class 8 and 9 combined. Advantages for stratifying in this way include: (i) the duration between identifying that an adolescent is depressed and the adolescent starting the intervention is minimised; (ii) a staggered start to the surveys meaning fewer research assistants are needed over the course of the trial; (iii) randomisation can be conducted after baseline with minimal delay. The randomisation will be done by a masked, independent researcher.

Masking and concealment

Research and clinical staff will work independently from separate offices in Chitwan. Figure 5 indicates which members of the trial team will be masked to allocation. Research assistants conducting baseline, midline, endline and follow-up surveys will not be given information about the allocation of schools. Due to the participatory nature of the intervention, adolescents, school staff, IPT facilitators and research assistants conducting the process evaluation will not be masked to allocation. The statistician conducting the final analysis of the pilot trial data will be masked. We will attempt masking at the cluster level: individual schools will not know if they have been allocated to the intervention or control.

Sample size

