The target estimand in the phase III trial is the participant-average treatment effect of IPT on student depression scores at endline, adjusted for clustering and municipality, population being all school students aged 13-19 within Chitwan. For this study summary data will be reported at the participant level rather than the cluster level as this gives the treatment effect for the average participant rather than cluster. Analysis will follow the intention to treat (ITT or treatment policy) strategy with students analysed according to their cluster randomised groups. Primary and secondary outcomes are continuous. The effect of treatment will therefore be the difference in mean outcomes between the treatment and control groups, adjusted for baseline depression score and clustering according to school and municipality. In the pilot trial the focus of the outcome analysis will be to generate effect sizes and confidence intervals (adjusted for clustering) for the treatment estimates. Relevant intercurrent events to the primary (and secondary) analyses are drop-out and adherence which are summarised as part of the feasibility assessment.

It is anticipated there will be sufficient numbers to run a version of the models for the phase III trial, a linear mixed model with depression scale (PHQ-A) as outcome, treatment group, time, baseline depression score and municipality as fixed effects and cluster as a random effect. The statistical estimate for treatment estimand is derived from the linear contrast between treatment groups at endline. One issue in the analysis of cRCTs is the impact of informative cluster size on the accuracy of the treatment effect estimate [27]. With different cluster sizes, participants in different sized clusters will have different weights and so will not contribute equally to the analysis. This might happen through differential drop-out between

the clusters and so drop-out will be described at the cluster and individual level. Also, recruitment (and therefore cluster size) may be better related to school level factors such as size of the school. An additional consideration is that there might be clustering by IPT group in addition to school level clustering, although with eight groups it is likely to be underestimated.

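### The pilot outcome model adjusts for municipality, which was not a randomisation factor, and leaves out the three strata within which schools were randomised

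*Protocol*

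**What the plan says.** Protocol, Randomisation: "Randomisation will be at the school level and stratified according to whether recruitment at the school includes adolescents from class 11 or not". The section continues: "In total there will be three strata". Strata 1 and 2 each hold two schools that recruit from classes 8, 9 and 11. For the third, "In Strata 3 there are four schools with two groups per school", recruiting from classes 8 and 9 only. The strata are taken in sequence. For Strata 1 the plan is to "randomise these schools with a 1:1 allocation ratio to the intervention and control arms", and the process is then repeated in the other two. Municipality is not mentioned in this section.

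Protocol, Planned analyses: municipality appears three times. It is in the phase III estimand, in the definition of the effect ("adjusted for baseline depression score and clustering according to school and municipality") and among the fixed effects of the linear mixed model, beside arm, time and baseline depression score, with school as the random effect. Stratum appears in none of these. The model is introduced as a form of the phase III model that the pilot should have enough data to run.

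Protocol, Design: the phase III primary analysis is to be "adjusted for baseline scores and potential confounders, and accounting for strata and clustering".

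**The concern.** When randomisation is restricted by stratum, the between-stratum part of the outcome variance cannot contribute to the error of the treatment comparison. A model without the strata leaves that part in the school-level residual. If strata differ in outcome, the standard error is then overstated and the interval covers more than its nominal 95%.

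Strata could plausibly differ here. They differ in age mix (class 11 or not), in planned school size and in start date, and CMOC 4 hypothesises that age affects benefit.

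Municipality gives no such protection. It was not balanced by design, so it can be correlated with arm by chance, and with eight schools that correlation can be large.

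What is at stake is the pilot's effect sizes and confidence intervals, which Planned analyses calls the focus of the outcome analysis, and the model that phase III would inherit.

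**Working it through.** **1. Design figures, from Randomisation and Sample size.** Schools × groups × 8 adolescents: 2×4×8 + 2×4×8 + 4×2×8 = 64 + 64 + 64 = 192. This reproduces the stated total. School sizes are 32 in Strata 1 and 2 and 16 in Strata 3.

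**2. Possible allocations.** One of two schools in Strata 1, one of two in Strata 2, two of four in Strata 3: 2 × 2 × 6 = 24.

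**3. School-level degrees of freedom, with eight schools.**
- Intercept, arm, municipality: 8 − 3 = 5 df, t(0.975) = 2.571.
- Intercept, arm, two stratum terms: 8 − 4 = 4 df, t = 2.776.
- Both: 8 − 5 = 3 df, t = 3.182.

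The stratum model gives the narrower interval only if it cuts the standard error to below 2.571/2.776 = 0.926 of its value under the municipality model.

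**4. Simulated interval widths.** School means were regressed on arm plus either municipality or stratum, with allocation drawn from the 24, t intervals and 6,000 runs per setting. The documents give none of the following, so they are assumptions: individual SD of 1, ICC of 0.01 to 0.10, between-stratum SD of 0 to 0.3 (taken as what remains after baseline adjustment), and no municipality effect. The split by municipality is also assumed: Strata 1 and half of Strata 3 in one municipality, Strata 2 and the other half in the other.

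Mean 95% interval width in SD units at ICC 0.05:

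| Between-stratum SD | Municipality | Stratum | Ratio | Coverage, municipality model |
|---|---|---|---|---|
| 0 | 1.12 | 1.15 | 0.97 | 95.4% |
| 0.1 | 1.16 | 1.15 | 1.01 | 96.1% |
| 0.2 | 1.29 | 1.16 | 1.11 | 96.6% |
| 0.3 | 1.47 | 1.16 | 1.27 | 97.6% |

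The stratum model covers about 95% throughout. At a between-stratum SD of 0.3 the ratio is 1.26/0.90 = 1.40 at ICC 0.01 and 1.66/1.41 = 1.18 at ICC 0.10. With no stratum effect it is 0.865/0.902 = 0.96 at ICC 0.01 and 1.369/1.400 = 0.98 at ICC 0.10. Break-even is near a between-stratum SD of 0.1. Fitting both terms at ICC 0.05 gives widths of about 1.45 to 1.47.

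**5. Dependence on the split by municipality.** With stratum means fixed at 0, 0.2 and 0.4 SD and ICC 0.05, the half-width under the municipality model ran from 0.55 to 0.77 over four assumed splits, against 0.56 with stratum. The low end arises if municipality happens to coincide with class 11 recruitment. With no stratum differences the range was 0.52 to 0.64 against 0.56.

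**6. Confounding with arm.** If each pair in Strata 1 and 2 has one school from each municipality and Strata 3 has two from each, 2 of the 24 allocations (8.3%) put all of one municipality in one arm. The stated model could then not separate municipality from treatment. Stratum cannot fail in this way, because every stratum contains both arms.

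**The case against.** The strongest reply is that little rides on this. Sample size says the pilot is not powered for depression, Planned analyses rules out between-group tests, the primary outcome is progression, and no criterion in Table 2 uses the model. That stands, and it limits the severity.

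It can also be said that the assumed stratum differences have no source in the Protocol. Strata 1 and 2 recruit the same classes in the same numbers, Figure 4 shows them two weeks apart, and baseline PHQ-A is already in the model. That also stands. A model with only a class 11 indicator would be slightly more precise than the three-level factor if Strata 1 and 2 are alike (half-width 0.52 against 0.56).

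Four stronger readings are tempting and are not supported:
- **The randomisation is not respected.** Schools are analysed as randomised under intention to treat, with school as a random effect. Arms are balanced within strata, so leaving strata out points to imprecision, not bias.
- **The intervals are too wide, without qualification.** This holds only if strata differ after baseline adjustment. With no difference the direction can reverse.
- **The ICC carried to phase III is inflated.** Sample size takes the ICC from baseline data, expects it to be biased downwards and triangulates it with other trials. It does not name the outcome model's variance component as the planning input.
- **The phase III estimand should name the pilot's strata.** The Protocol does not set out the phase III design, and the pilot's waves need not recur there.

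**Conclusion.** The point holds as a mismatch between randomisation and analysis and as a contradiction between Design and Planned analyses. The pilot model carries a factor that was not used in randomisation, without a reason, and omits the one that was.

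The numerical consequence is conditional. For the split assumed in the table, at ICC 0.05, intervals are about 11% to 27% too wide if the between-stratum SD left after baseline adjustment is 0.2 to 0.3, and about 3% narrower if there is none. These figures describe an assumed scenario at school level, not the full mixed model, and they move with the unstated split of schools by municipality.

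This should be fixed because the correction is cheap and the model is the template for phase III. It is not critical, because the progression decision does not use it.

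**What to change.** In Planned analyses, replace municipality with the three-level randomisation stratum as a fixed effect in the pilot effect definition and mixed model. Keep municipality, if wanted, as a sensitivity analysis with a stated reason. Do not fit both in the main model, since that leaves 3 school-level df.

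Reconcile Design and Planned analyses by saying that the phase III analysis will adjust for whatever factors phase III randomisation is stratified by. Do not write the pilot's strata into the phase III estimand.

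The cost is wording and one school-level degree of freedom. The t multiplier rises from 2.571 to 2.776 (2.776/2.571 = 1.08). If strata do not differ, the interval is about 2–4% wider under the split used in the table (1.400/1.369 = 1.02 at ICC 0.10 to 0.902/0.865 = 1.04 at ICC 0.01). Trial status says endline and follow-up surveys were still under way, so the change should be dated and made before the outcome analysis.

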School-based group interpersonal therapy for adolescents with depression in Nepal: a pilot realist cluster-randomised controlled trial

Study protocol

Version 2.3.1 Version 2.3 started: 05/07/2024

ISRCTN14652885

Revision History

Document ID - (Title)	Description of changes from previous revision	Effective
revision X.Y		Date
2.2	Revision to adolescent recruitment policy	
	Revised caregiver sample from 100% to ~30%	
	subsample of participating adolescents	
	Three strata rather than two	
2.3	Edit to progression criteria language –	
	addition of the word eligible ["Percentage of	
	eligible adolescents with informed consent at	
	baseline"]	
	Amendment to inclusion criteria – changed from	
	>=10 to >=11 based on validation study findings	
	To avoid ceiling effects we increased time period	
	over which we record attendance from 12 to 18	
	days. Revised outcome is: "Number	
	of days attended in the 12 school days prior to the	
	baseline (excluding school closures and	
	Saturdays).	

Table of Contents

Revision History	2
Trial registration	6
General information	6
Funder	6
Sponsor reference	6
Trial Steering Committee	6
Background	7
Psychological interventions	7
Interpersonal therapy (IPT)	7
IPT in Nepal	8
Realist cluster randomised trials	8
Theory of change for interpersonal therapy for adolescents with depression in Nepal	9
Research aims and questions	10
Progression criteria	10
Pilot trial design and methods	11
Setting	11
Design	11
Inclusion/exclusion criteria	12
Randomisation	13
Masking and concealment	
Sample size	14
Intervention	
Recruitment and training of IPT facilitators	
Comparator – control condition	
Recruitment	
Trial outcomes and measurement	17

Intercurrent events
Planned analyses
Process evaluation
CMOCs21
Cost analysis
Incentives
Post-trial care
Ethics
Harms
Trial registration and conduct
Dissemination
Timeline
Trial status
Tables
Figures
References

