2; all adolescents in Class 8 and 9 in Strata 3. Adolescents will be instructed to bring the consent form back by a certain date if they are interested in being screened and potentially participating in the trial. Research assistants will explain that signing the consent form will not guarantee their participation in the research as we will only recruit a certain number of students who meet the eligibility criteria. In each school in Strata 1 and 2 we will randomly order adolescents who return consent forms signed by their parents, and screen adolescents as per this random order until we recruit the desired number of participants. We will create one random order for adolescents with signed consent forms in Class 8 and 9 and a separate random order for adolescents in Class 11. In these schools we will recruit sufficient adolescents to form one boys' and one girls' IPT group across Class 8 and 9, and one boys' and one girls' group from Class 11 (four groups per school). In each of the four Strata 3 schools we will randomly order adolescents in Class 8 and 9 who return consent forms and screen as per the order until we have sufficient participants for one boys' and one girls' group (two groups per school).

Trial outcomes and measurement

The primary outcome of the pilot trial is progression to the phase III trial based on the progression criteria. The target primary outcome for the phase III trial is depression symptoms measured as a continuous outcome. Target secondary outcomes are functional impairment, anxiety, post-traumatic stress disorder and school attendance. Table 3 presents all the outcomes and tools to measure them.

Data collection, management and monitoring

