We will do an activity-based cost analysis of the implementation of IPT from the provider perspective. Costs from monthly project accounts will be entered in an Excel tool, divided into start-up or implementation costs, and allocated to different cost centres (capital, staff, and materials) and intervention activities (e.g. adaptation, training, facilitation, etc.). Through interviews with project staff members, we will collect information about how they divided their time across activities and thus how to allocate their salaries. The total cost of the intervention will be annualised then divided by the number of participants in a year to estimate a unit cost per IPT participant.

Incentives

We will cover transportation costs incurred by adolescents and adults participating in the process evaluation and they will also be offered refreshments (juice and biscuits). Phone credit will be offered as an incentive to adolescents and caregivers participating in the surveys.

Post-trial care

Where required, a psychosocial counsellor employed by TPO Nepal will remain in the study setting to provide follow-up care for participants.

Ethics

We have ethical approval from the Nepal Health Research Council (ref no. 701) and King's College London Research Ethics Committee (HR/DP-22/23-37705).

At the school level, we will take written consent from the school principal to screen adolescents and for randomisation. Eligible adolescents who wish to participate in the trial will be asked to take home a written information sheet and consent form. We will obtain written consent from adolescents which will be collected before the baseline survey is conducted. For adolescents aged 17 and younger we will take consent from their caregiver

and adolescent assent. We will obtain written consent from any caregiver, teacher or IPT facilitator from whom we collect data.

Disclosures of suicidality will be handled according to the type of participant.

i) Trial participants

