There are no anticipated harms for participants or schools but there may be unanticipated harms. We will assess these by analysing outcomes at endline and follow-up, by collecting information on any adverse events, and exploring potential harms through the qualitative interviews and FGDs in the process evaluation. King's College London is the sponsor. There will not be a Data Safety and Monitoring Board (DSMB) for the pilot trial. Any serious adverse events will be reported immediately to the Trial Steering Committee (TSC) who will decide what action should be taken. We will report other adverse events to the TSC at follow-up.

Trial registration and conduct

We have registered the trial with the ISRCTN registry. We will follow MRC Guidelines for Global Health Trial Management.

Dissemination

We will publish findings from the pilot trial including the process evaluation and analysis of realist data in academic journals. We will organise dissemination events in Chitwan and Kathmandu, with national and local government officials, adolescents, caregivers, teachers, researchers and non-governmental organisations.

Timeline

Figure 7 presents the SPIRIT enrolment, intervention and assessment schedule.

Trial status

As of July 2024, recruitment is complete. IPT groups have finished in all three strata. Endline and follow-up surveys are ongoing.

Tables

Table 1: Research questions and data sources

Question	Data sources
Is it feasible to deliver IPT in	Proportion of planned IPT sessions delivered
secondary schools in Chitwan?	Focus group discussion and interview transcripts with IPT facilitators, adolescents, teachers
	and caregivers
Is the intervention acceptable to	Proportion of adolescents who consent to participate in the trial
participants?	Proportion of IPT sessions attended by intervention participants
	Proportion of all schools invited who agree to participate in the trial
	Intervention participant treatment satisfaction surveys
	Focus group discussion and interview transcripts with intervention participants
Is the intervention acceptable to	Focus group discussion and interview transcripts with caregivers and teachers
caregivers and teachers?	
Is it feasible to train and supervise	Therapeutic competency assessed with ENACT and GroupACT tools
local lay people to deliver IPT?	Intervention fidelity assessed with the IPT checklist
	Proportion of facilitators trained who pass a paper-based IPT knowledge test

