	Serious adverse events	Percentage difference in serious adverse	<4	4	5
		events in the intervention arm compared			
		to the control arm			
Are trial procedures	Eligible adolescents	Percentage of eligible adolescents with	>80%	50-80	<50
(randomisation and data	agree to participate	informed consent at baseline			
collection) acceptable to	Eligible schools agree to	Percentage of schools approached that	>60%	30-60	<30
participants and schools?	participate	agree to participate			
	Missing data	Percentage of missing items on primary	<15	15-50	>50
		and secondary outcome			
	Participant retention	Percentage of participants completing	>70%	30-70	<30
		the endline survey			
	t .		1	-1	

Table 3: Potential outcomes and tools

Outcome type	Outcome	Assessment timepoint	Potential tools	Notes
In-session	Depression	Start of each pre-group and group session	IPT-A in-session weekly symptom check	7 items, response options presented as emojis
	Satisfaction	Endline	Treatment satisfaction	Adapted from Mufson 2015.
Primary	Depression	Baseline, midline1, midline 2, endline and follow up	PHQ-A MMAP trans	
Secondary	Functional impairment	Baseline, midline1, midline 2, endline and follow up	Locally developed tool	Adapt for Chitwan and for boys and girls
	Anxiety	Baseline, endline and follow-up	Generalised Anxiety Disorder Assessment (GAD-7)	MMAP translation
	Post-traumatic stress disorder	Baseline, endline and follow-up	PCL-C (8-item abbreviated version of the PTSD Checklist 5)	
	School attendance	Baseline and endline	Number of days attended in the 18 school days prior to the baseline (excluding school closures and Saturdays)	Collect data from school register
	Educational performance	Endline	End of year examination	
	Quality of Life	Baseline and endline	EuroQol-5 Dimension 5 levels (EQ-5D)	
Intermediate	Норе	Baseline, midline 1, midline 2, endline, follow-up	Children's Hope Scale	6 items
	Emotion regulation	Baseline, midline 1, midline 2, endline, follow-up	Difficulties in Emotion Regulation Scale (DERS-SF) 18 items	Used in ALIVE

	Self efficacy	Baseline, midline 1, midline 2, endline, follow-up	General Self-efficacy Scale	
	Social support	Baseline, midline 1, midline 2, endline, follow-up	Multidimensional Scale of Perceived Social Support	Need to add to battery
	Group cohesiveness	(intervention group only) Midline 1, midline 2, endline, follow-up	PM+ Group Cohesiveness scale	Used in PM+
	IPT skills	Midline 1, midline 2, endline, follow-up	Interpersonal Psychology Skills Scale	

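### The Table 2 consent criterion measures only refusal after screening, so under the Recruitment procedure it cannot signal poor uptake at the consent-form stage

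*Protocol*

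**What the plan says.** **Criterion.** In Protocol, Table 2, the row on whether eligible adolescents agree to participate uses an indicator starting "Percentage of eligible adolescents with" and continuing with informed consent at baseline. Green is above 80%, amber 50-80%, red below 50%. Under Trial outcomes and measurement, progression judged on these criteria is the pilot's primary outcome.

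**Eligibility.** Protocol, Inclusion/exclusion criteria, requires adolescents "with depression (i.e. scoring 11 or more on the PHQ-A); and" a functional impairment score of 4 or more. Both scores come from screening.

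**Order under Recruitment.** Forms are offered to all adolescents in the target classes, who are told to "bring the consent form back by a certain date if they are interested in being screened and potentially participating in the trial". For the first two strata the text reads: "we will randomly order adolescents who return consent forms signed by their parents, and screen adolescents as per this random order". For the third stratum it reads: "we will randomly order adolescents in Class 8 and 9 who return consent forms and screen as per the order".

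**Order under Ethics.** The principal consents to screening, and then "Eligible adolescents who wish to participate in the trial will be asked to take home a written information sheet and consent form". The adolescent's own consent, or assent with caregiver consent at age 17 and younger, is collected before the baseline survey.

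**Version history.** The Revision History lists under version 2.3, started 05/07/2024, an "Edit to progression criteria language" that added the word *eligible*. Trial status says "As of July 2024, recruitment is complete".

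**The concern.** A consent rate is useful for progression if its denominator includes the people who said no. Under Recruitment, the main opportunity to say no is not returning the form. Adolescents who do that are never screened, so their eligibility is never known and they cannot be counted among the eligible. The denominator is therefore already restricted to families who agreed at the form stage.

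This matters because it is the only banded criterion in Table 2 on adolescents' willingness to enter. Adherence, satisfaction and retention are all measured after enrolment. The neighbouring school criterion divides by schools approached, which is the kind of denominator missing here. A green light on this row could be read as evidence that adolescents and families accept the trial when the row has not measured it.

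**Working it through.** **Plan's own figure.** Strata 1: 2 schools x 4 groups x 8 = 64. Strata 2: the same, 64. Strata 3: 4 schools x 2 groups x 8 = 64. The total is 192, as stated under Sample size. The protocol gives no expected value for the consent percentage, only the bands.

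**Symbols.** The protocol gives none of these values, so they are assumptions:
- N: adolescents offered a form
- e: share of them who are truly eligible
- u: form-return rate among the eligible
- s: share of returned forms reached in the random order before the quota is filled
- d: share of screened eligible adolescents who decline before baseline

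**Indicator under the Recruitment order.**
- Denominator (known eligible): N·e·u·s
- Numerator (eligible with consent at baseline): N·e·u·s·(1 - d)
- Ratio: 1 - d

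The return rate u cancels, and so do N, e and s. Stopping at the quota does not change the result.

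**Share of all eligible adolescents offered a form who would agree at both stages.** This is u·(1 - d). The bands were written for eligible adolescents, so they can be applied to this quantity for comparison, although it cannot be observed under the Recruitment order.

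| u (assumed) | Indicator as worded, d from 0 to 10% | u·(1 - d), d from 0 to 10% |
|---|---|---|
| 10% | 100% to 90%, green | 10% to 9%, red |
| 30% | 100% to 90%, green | 30% to 27%, red |
| 50% | 100% to 90%, green | 50% to 45%, amber to red |
| 80% | 100% to 90%, green | 80% to 72%, amber |

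**Refusals needed to change the light, with 192 recruited.**
- To leave green: 192/(192 + x) ≤ 0.80 gives x = 48 (192/240 = 80%, which is not above 80%).
- To reach red: 192/(192 + x) < 0.50 gives x = 193 (192/385 = 49.9%).

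All of these refusals must come from adolescents who have already returned a form and been screened.

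**Indicator under the Ethics order.** If screening rests on the principal's consent and forms go home only with those found eligible, non-returners are known to be eligible and stay in the denominator. The indicator is then sensitive to u. The same row therefore means two different things depending on which section was followed.

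**The case against.** **The indicator is not a tautology.** The forms described for Strata 1 and 2 are signed by parents, and Ethics asks separately for the adolescent's own consent or assent before baseline. A screened, eligible adolescent can still refuse. This stands: the indicator is 1 - d, not a constant. A reader might infer that it is green whatever happens, but it leaves green once 20% or more of screened eligible adolescents decline.

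**Low uptake is not hidden altogether.** Table 1 lists the share of adolescents who consent without restricting it to the eligible, and recruitment rates by gender, school and age. This also stands, but neither carries a band, so neither can turn a light amber or red.

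**Forms returned out of forms offered measures something else.** That denominator includes adolescents without depression. The point is fair, and it means the present bands cannot simply be carried over. A low return rate among all students would not by itself be red on bands set for eligible adolescents.

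**The link to phase III size is loose.** Sample size says the recruitment rate is estimated from the pilot and triangulated with other trials, and the criteria only inform the decision. Nothing says that this row sets the number of schools or students to approach, so that consequence is not claimed here.

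**Timing.** Set beside the Trial status statement, the version 2.3 date might lead a reader to infer that the denominator was changed after recruitment ended. The documents do not establish that. The date is when the version was started, and no effective date is shown. The same entry records the change in the PHQ-A threshold and in the baseline attendance window, which would ordinarily apply at screening and baseline. The row's title already speaks of eligible adolescents, so the edit may be a clarification.

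**Conclusion.** The point holds for the Recruitment order, which is the more detailed account and covers all three strata. Followed that way, the criterion captures only refusal between screening and baseline. It stays green unless about 20% or more of screened eligible adolescents decline (48 or more if 192 are recruited), and the form-return rate has no influence on it. It cannot signal poor uptake at the consent-form stage.

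The algebra needs no assumed values. The return and refusal rates in the table are illustrations. The conclusion would not apply if the Ethics order was the one used, and the protocol does not settle which was. The two sections contradict each other and must be reconciled before this row is read. The conclusion does not depend on when the word *eligible* was added, and no finding of a post-recruitment change is made.

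**What to change.** 1. State which order was followed and bring Recruitment and Ethics into line. If it was the Ethics order, the indicator can stand once Recruitment is corrected.
2. If it was the Recruitment order, base the uptake criterion on forms returned out of adolescents offered a form, overall and by school, sex and class. Report the eligible-to-baseline fraction separately as description.
3. Because the new denominator includes adolescents without depression, either justify bands for it or declare the criterion not assessable rather than green.
4. State when and why the word *eligible* was added in version 2.3.

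**Cost.** The change is to wording and to one count. The random-order lists are lists of form-returners, so they should supply the numerator. Class enrolment can stand in for forms offered, since every adolescent in the target classes was to be offered one. The indicator will look less favourable, and comparability with the existing bands is lost.
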